**Statistical Analysis Plan**

---

binding method) in order to control the overall Type I error.

The IA will take place after the first 184 events (75% of planned DFS events as assessed by the IRC) have occurred. If the event occurrence pace is much slower than anticipated, the IA could be performed with less than 184 events observed (<75% of the total required) at the sponsor's discretion with the Data Monitoring Committee's consensus.

The objectives of the IA are:

- To assess safety, including unexpected toxicity.
- To allow for early stopping of the trial due to futility.
- To allow for early stopping of the trial due to efficacy.

If the results of the IA demonstrate statistically significant differences between the 2 treatment arms for DFS (in favor of the active drug), the sponsor, in consultation with HRAs, will disseminate the results of the trial, and the IA may be considered the final analysis for DFS. The nominal level of significance for the interim analysis of DFS determined using the Lan DeMets procedure with an O'Brien Fleming type stopping rule will be 0.0194 (2-sided; if the interim analysis is performed at 184 events).

The descriptive safety analysis as described in Section 7.5 will be presented to assess any toxicities.

The nominal significance level for the interim futility analysis of DFS will be determined using an O'Brien-Fleming stopping boundary. The futility p-value boundary is specified in the table below. If the calculated futility p-value is greater than the pre-specified boundary shown in the table below, the sponsor may choose to stop the trial for futility. The associated critical hazard ratio is also provided in the table below for reference.

**Futility Stopping Boundary (non-binding) for DFS for Rejecting Alternative Hypothesis  
 Expressed as HR and p-value**

| Analysis | Fraction of DFS Events | Number of DFS Events | HR (Axitinib:Placebo) | 2-sided p-value |
|----------|------------------------|----------------------|-----------------------|-----------------|
| Interim  | 75%                    | 184                  | 0.836                 | 0.2255          |

The overall nominal significance level for the efficacy analysis of DFS will be preserved at 0.05 (2-sided test). To protect the integrity of the study and to preserve the type 1 error, a fraction of alpha will be spent at the interim analysis based on an O'Brien-Fleming stopping boundary. The efficacy p-value boundaries are specified in the following table. The associated critical hazard ratio is also provided in the table below for reference.

---

Document: C:\Users\q764206\AppData\Local\Microsoft\Windows\Temporary Internet Files\Content.Outlook\GWW33WM3\ATLAS\_SAPFinal v8.0\_06MAR2018.docx  
 Author: [name] (Updated [name]; [name]; [name], [name])      Version Number: Final 8.0

Version Date: 06MAR2018

Template No: CS\_TP\_BS016 – Revision 2  
 Effective Date: 01Feb2010

Reference: CS\_WI\_BS005

Statistical Analysis Plan

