#### 9.5. Interim Analysis

A single interim analysis (IA) will be performed in the study. O'Brien – Fleming type stopping boundaries based on the Lan-DeMets spending function will be applied. Futility criteria are not used to calculate the nominal alphas (non-binding method) in order to control the overall Type I error.

The interim analysis will take place after the first 184 events (75% of the events as assessed by the IRC) have occurred. If the event occurrence pace is much slower than anticipated, the IA could be performed when less than 184 events observed (<75% of the total required) at sponsor's discretion with the Data Monitoring Committee's (DMC) consensus.

The objectives of the interim analysis will be:

1. To assess safety, including any unexpected toxicity. If the results of the interim analysis indicate serious safety concerns, the Sponsor will consult with HRAs regarding stopping the clinical trial.

- 2. To allow for early stopping of the trial due to futility. If the conditional power is low, the sponsor may choose to stop following up patients. Conditional power calculations will be performed using SAS Version 9.2. Criteria for futility will be provided in SAP.
- 3. If the results of the interim analysis demonstrate statistically significant differences between the 2 treatment arms for DFS, the sponsor, in consultation with HRAs, will disseminate the results of the trial, and the interim analysis may be considered the final analysis for DFS. The nominal level of significance for the interim analysis of DFS determined using the Lans-DeMets procedure with an O'Brien-Fleming type stopping rule will be 0.0194 (if the interim analysis is performed at 184 events).

The following table summarizes the nominal significance level (2-sided) at each analysis when 75% and 100% of events are observed at the interim analysis and the final analysis.

Fraction of total events	Nominal α level
75%	0.0194
100%	0.0442

The actual nominal  $\alpha$  levels for the interim analysis and for the final analysis will depend on the fraction of total events occurred at the time of interim analysis.

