**Statistical Analysis Plan**

---

thereafter for the remainder of the follow-up period. The total duration of the study from first subject in to final analysis is estimated to be 5 years.

All subjects will be followed for OS status (regardless of the duration of treatment) every 16 weeks until the time of final DFS analysis. Survival status can be ascertained by telephone contact. At the time of final DFS analysis, OS results will be analyzed and summarized.

A single interim analysis (IA) of efficacy and safety will be performed after approximately 184 DFS events (approximately 75% of the total number of required events as assessed by the independent review committee [IRC]) have occurred. If the event occurrence pace is much slower than anticipated, the IA could be performed when less than 184 events are observed (<75% of the total required) at the sponsor’s discretion with the Data Monitoring Committee’s (DMC) consensus. To protect the integrity of the study and to preserve the Type 1 error, a fraction of alpha will be spent at the interim analysis of DFS based on an O’Brien-Fleming spending function. The stopping boundaries will be calculated based on the actual number of events at the time of the interim analysis.

The objectives of the interim analysis will be:

- To assess the safety, including any unexpected toxicity.
- To allow for early stopping of the trial due to futility.
- To assess the efficacy of the study drug to allow stopping of trial for success of efficacy.

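### The interim futility criterion is a 2-sided p-value with no direction, so as written it is not met for observed hazard ratios above about 1.196

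*SAP*

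**What the plan says.** The futility rule is in SAP section 6.3. Its operative sentence reads "If the calculated futility p-value is greater than the pre-specified boundary shown in the table below", in which case "the sponsor may choose to stop the trial for futility". The table is headed "Futility Stopping Boundary (non-binding) for DFS for Rejecting Alternative Hypothesis", and the rest of the heading says the boundary is expressed both as an HR and as a p-value. Its last two columns are "HR (Axitinib:Placebo) | 2-sided p-value", and its single row, for 184 events, gives 0.836 and 0.2255. On the role of the HR the SAP says: "The associated critical hazard ratio is also provided in the table below for reference".

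Neither document defines the term futility p-value. The efficacy paragraph of the same section requires the difference to favour axitinib; the futility sentence has no such condition.

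Protocol section 9.5 gives the aim: "If the conditional power is low, the sponsor may choose to stop following up patients". It then leaves the rule to the SAP: "Criteria for futility will be provided in SAP". The SAP gives no conditional-power threshold, so this sentence and table are the whole futility specification.

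**The concern.** A 2-sided p-value measures distance from HR = 1 in either direction. It is large near HR = 1 and falls again as the result moves against axitinib. A rule that signals futility when this p-value is large therefore stops signalling once the result is bad enough. That runs against the aim in the protocol, because conditional power is lowest exactly there.

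The SAP makes the p-value the criterion and the HR a reference, so a reader who follows the text gets one answer from the p-value and the opposite one from the HR in the same row. What is at stake is whether the DMC and the sponsor receive an unambiguous statement that the boundary was or was not crossed. The type I error is not at stake.

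**Working it through.** **Inputs.** From SAP 6.3: 184 interim events, futility p 0.2255 with HR 0.836, interim efficacy p 0.0194 with HR 0.708, final p 0.0442 with HR 0.773 at 245 events. From SAP 3.3: 1:1 allocation and design HR 0.654.

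**1. Reproduce the tabulated HRs.** With 1:1 allocation, SE(ln HR) = 2/√events and the critical HR is exp(−z × SE).

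- Futility: SE = 2/√184 = 0.1474; z = Φ⁻¹(1 − 0.2255/2) = 1.2120; HR = exp(−1.2120 × 0.1474) = 0.836, as tabulated.
- Efficacy: p 0.0194 at 184 events gives 0.708, and p 0.0442 at 245 events gives 0.773, both as tabulated.
- Had 0.2255 been a 1-sided value, the HR would be 0.895. The figure is therefore an ordinary 2-sided p-value.

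**2. Range in which the criterion is met.** 2-sided p > 0.2255 means |z| < 1.2120, so the observed HR lies between 0.836 and 1/0.8364 = 1.196.

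**3. Compare the two columns.** Here Z = −ln(HR) × √184/2, so positive values favour axitinib. Conditional power (CP) is taken under the design HR, with t = 184/245 = 0.751, final critical value 2.012 and drift −ln(0.654) × √245/2 = 3.323:

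CP = 1 − Φ((2.012 − Z√t − 3.323(1 − t))/√(1 − t))

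| Observed HR | Z | 2-sided p | p > 0.2255 | HR > 0.836 | CP |
|---|---|---|---|---|---|
| 0.80 | 1.513 | 0.130 | no | no | about 60% |
| 0.90 | 0.715 | 0.475 | yes | yes | 12.9% |
| 1.25 | −1.513 | 0.130 | no | yes | 2.8 × 10⁻⁷ |
| 1.30 | −1.779 | 0.075 | no | yes | 2.3 × 10⁻⁸ |

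HRs of 0.80 and 1.25 have the same p-value, so the written rule treats them alike. The HR column separates them.

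**4. How often this matters.** If the true HR is 1.0:

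- P(2-sided p > 0.2255) = 1 − 0.2255 = 0.7745
- P(observed HR > 0.836) = Φ(1.212) = 0.8873
- The difference, 0.1128, is the chance of an observed HR above 1.196.

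That chance is about 29% if the true HR is 1.1 and 51% if it is 1.2. Under the design HR of 0.654 it is about 2 × 10⁻⁵ (0.002%).

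**5. Meaning of 1.196.** Its approximate 95% interval is exp(0.1787 ± 1.96 × 0.1474), or 0.90 to 1.60. It is not in itself evidence of harm.

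**The case against.** The strongest reply is that nobody would misread this table. The two cells describe one boundary point and agree exactly. The heading speaks of rejecting the alternative and presents the HR and the p-value as two expressions of the same limit. Rejecting HR 0.654 cannot sensibly mean stopping at 0.90 but not at 1.30. The conflict arises only when an undefined p-value is carried into the opposite tail. The boundary is also non-binding, the DMC sees unblinded data, the sponsor can end the trial at its discretion (protocol section 14), and nothing obliges the trial to continue when the criterion is not met. On this view the comparison of 77% with 89% sets the intended rule against one that nobody intended.

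Most of this stands, and it limits the weight of the point. The intent is clear, and a sensible DMC would act on it. It does not repair the text: the SAP names the p-value as the criterion and the HR as a reference, and it states direction for efficacy but not for futility. The tabulated HR also applies only at 184 events. The interim may be held earlier, and SAP 3.1 then recalculates: "The stopping boundaries will be calculated based on the actual number of events at the time of the interim analysis". Direction should therefore be part of the rule and not be left to inference from one HR cell.

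**Conclusion.** The concern holds. As written, the futility criterion at 184 events is met only for observed HRs from 0.836 to 1.196, and above 1.196 it contradicts its own reference HR. The disagreement covers 11.3% of trials if the true HR is 1.0. It includes the results with the lowest conditional power, which are the ones protocol 9.5 wants identified.

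This rests on reading the futility p-value as the ordinary 2-sided log-rank p-value, which the tabulated HR supports, and on the 2/√events approximation; the stratified test may move the limits slightly. The consequence is modest: the rule is non-binding and discretionary, its intent can be recovered, and no efficacy boundary depends on it. It should be corrected, but it does not threaten the primary inference.

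**What to change.** In SAP 6.3, state the criterion with its direction: the futility boundary is crossed if the observed HR (axitinib:placebo) exceeds the critical HR, equivalently if the 1-sided p-value for axitinib benefit exceeds half the tabulated 2-sided value. At 184 events these are 0.836 and 0.2255/2 = 0.1128. Relabel the p-value column of the futility table to match.

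Name one of the two as decisive, because rounding can separate them at the margin: an HR of exactly 0.836 corresponds to a 2-sided p of 0.2244. Add that both values are recalculated if the interim is not at 184 events; a cross-reference to SAP 3.1 is enough.

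The cost is one sentence and one column label. Alpha is unchanged because the futility boundary is not used in setting the efficacy levels. Power is essentially unchanged, since under HR 0.654 the two versions differ in about 0.002% of trials. Protocol 9.5 needs no amendment for this point because it leaves the futility criteria to the SAP.

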**Efficacy Stopping Boundary for DFS for Rejecting Null Hypothesis Expressed as HRs and p-values**

| Analysis | Fraction of DFS Events | Number of DFS Events | HR (Axitinib:Placebo) | 2-sided p-value |
|----------|------------------------|----------------------|-----------------------|-----------------|
| Interim  | 75%                    | 184                  | 0.708                 | 0.0194          |
| Final    | 100%                   | 245                  | 0.773                 | 0.0442          |

The actual nominal  $\alpha$  levels for the interim analysis and for the final analysis will depend on the fraction of total events occurred at the time of the IA.

In addition to DFS based on IRC assessment, Kaplan-Meier summaries for DFS (according to investigator assessment) and OS will be presented for each treatment group.

The primary endpoint of DFS is based on IRC assessment. DFS based on investigator assessment is an important sensitivity analysis. Although no formal hypothesis testing is planned for DFS based on investigator assessment, regulatory feedback has indicated the importance of consistency between investigator and IRC assessments of DFS. Therefore, in order to meet the criteria for stopping for efficacy at the time of the interim analysis the same p-value stopping criteria, determined based on the proportion of IRC assessed events at the time of the interim analysis out of the planned 245 events for the final analysis, will be applied to DFS based on investigator assessment. Specifically, both the primary DFS analysis by IRC assessment and the DFS analysis by investigator assessment must meet the stopping criteria to stop for efficacy at the time of the interim analysis. Assuming 184 IRC assessed events at the time of the interim analysis both the IRC and investigator DFS 2-sided p-values will be required to fall below 0.0194 to stop the study for efficacy. The stopping rule for futility will only be applied to the primary DFS analysis by IRC assessment.

Although there is no intention to perform any hypothesis test for OS at the interim analysis, a nominal  $\alpha$  of 0.0001 will be allocated to the analysis of OS at the interim. The overall nominal significance level for the efficacy analysis of OS will be preserved at 0.05 (2-sided test).

Note that for the interim analysis, the data will be initially presented to members of the DMC and designated unblinded personnel only. Decisions and recommendations based on the interim analysis review will be disseminated to the sponsor. The sponsor at that time may review and discuss the DMC recommendations with a second panel of independent experts.

There are also planned regular reviews of the safety at separate DMC meetings as needed. Safety data will be summarized as described in Section 7.5. The timing and details of the DMC review are detailed in the DMC charter.

**6.4. Multicenter Studies**

No adjustment will be made in any analyses for center.

---

|                 |   |                 |             |
|-----------------|---|-----------------|-------------|
| Document:       | C:\Users\q764206\AppData\Local\Microsoft\Windows\Temporary Internet Files\Content.Outlook\GWW33WM3\ATLAS_SAPFinal v8.0_06MAR2018.docx |                 |             |
| Author:         | [name] (Updated [name]; [name]; [name], [name])  | Version Number: | Final 8.0   |
|                 |   | Version Date:   | 06MAR2018   |
| Template No:    | CS_TP_BS016 – Revision 2  | Reference:      | CS_WI_BS005 |
| Effective Date: | 01Feb2010   |                 |             |

Statistical Analysis Plan

---

**6.5. Multiple Comparisons/Multiplicity**

For the interim analysis performed and the final analysis for the primary endpoint of DFS, the significance level has been set using the O’Brien-Fleming method. Although there is no intention to perform any hypothesis test for OS at the interim analysis, a nominal  $\alpha$  of 0.0001 will be allocated to the analysis of OS at the interim. There will be no other adjustments for multiple testing.

**7. Statistical Analysis**

**7.1. Analysis of Primary Efficacy Endpoint**

**7.1.1. Disease-Free Survival Based on IRC Review**

Disease-Free Survival of the ITT Population based on the IRC review of tumor assessments will be summarized using the Kaplan-Meier method. Kaplan-Meier curves for each arm will be generated, and median DFS time will also be presented with corresponding 95% CI. The CI for the median will be calculated according to Brookmeyer and Crowley. To test the equality of DFS time in each arm a stratified log-rank test (using a stratification factor as defined in Section 5.4) will be used. Censoring rules as described in Table 1 of Appendix A will be implemented. The statistic of the test will be presented along with the associated two-sided p-value.

The estimated HR (Axitinib/Placebo) will be obtained using a Cox’s Proportional Hazards model with treatment group as well as a randomization stratification factor as a covariate. The stratification factor used in the analyses will be risk group as described in Section 5.4.1.

The significance level for the final DFS analysis will be 0.0442 as calculated using the O’Brien-Fleming method. (Assumes interim analysis at 184 events with a significance level of 0.0194).

Annual DFS rates up to 5 years for each treatment group will be estimated and presented with corresponding 95% CI. The CI for the survival function will be calculated using the complementary log-log transformation method.

The final analysis of the primary endpoint of DFS will be performed when approximately 245 DFS events based on IRC review are observed.

A subject listing for DFS will include, DFS time, censoring status, censoring reason, date of randomization and date of last tumor assessment. In addition, a listing of subjects with baseline disease as determined by the IRC, will be produced.

**7.1.2. Methods for Evaluating the Validity of Model Assumptions**

---

|           |   |                 |           |
|-----------|---|-----------------|-----------|
| Document: | C:\Users\q764206\AppData\Local\Microsoft\Windows\Temporary Internet Files\Content.Outlook\GWW33WM3\ATLAS_SAPFinal v8.0_06MAR2018.docx |                 |           |
| Author:   | [name] (Updated [name]; [name]; [name], [name])  | Version Number: | Final 8.0 |
|           |   | Version Date:   | 06MAR2018 |

|                                       |                        |
|---------------------------------------|------------------------|
| Template No: CS_TP_BS016 – Revision 2 | Reference: CS_WI_BS005 |
| Effective Date: 01Feb2010             |                        |

**Statistical Analysis Plan**

---

Schoenfeld residuals for the stratified Cox proportional regression model will be plotted to investigate graphically violations from the proportional hazards (PH) assumption for the primary DFS endpoint; a non-zero slope is evidence of departure from PH. The PH assumption will be formally tested using Schoenfeld’s residual test (Schoenfeld, 1980; Therneau and Grambsch, 2000). Large departures from PH will be evidenced by a p-value < 0.05.

In addition, the proportional hazards assumption will be checked visually by plotting

$-\log(\log(S(t)))$  versus  $\log(t)$ ,

where  $S(t)$  is the estimated survival function at time  $t$ .

If these assessments show large departures from proportional hazards, then DFS may also be analyzed based on the test of RMST( $\tau$ ) differences between treatment arms based on the stratified Cox regression model as described in Zhang (2013).

The RMST up to time  $t^*$  can then be interpreted as the expected survival time restricted to the common follow-up time  $t^*$  among all patients. Analyses will be repeated using the follow criteria to define  $t^*$ :

- $t^*1$  = min of (longest observed survival time for experimental arm, longest observed survival time for control arm) in years
- $t^*2$  = min of (longest event time for the experimental arm, longest event time for the control arm) in years
- $t^*3$  = the midpoint between the numbers  $t^*1$  and  $t^*2$

RMST can be estimated consistently by the area under the Kaplan-Meier curve over  $[0, t^*]$ . The treatment effect between each of the experimental arms and the control arm will be assessed based on the difference in RMST. The associated 95% CI for the difference in means and two-sided p-value will be generated. RMST as a function of  $t^*$  and the associated treatment effect between each of the experimental arms and the control arm will be plotted against time  $t^*$ .

Note RMST was not specified in the protocol. This was added to the SAP as an exploratory analysis.

**7.2. Analysis of Secondary Efficacy Endpoint**

**7.2.1. Overall Survival (OS)**

OS of the ITT Population will be analyzed in the same way as the primary endpoint. Censoring rules as described in Table 2 of Appendix A will be implemented. At the time of final analysis of DFS, a hypothesis test on OS will be conducted at two-sided  $\alpha = 0.0499$  only if DFS is

---

|           |   |                 |           |
|-----------|---|-----------------|-----------|
| Document: | C:\Users\q764206\AppData\Local\Microsoft\Windows\Temporary Internet Files\Content.Outlook\GWW33WM3\ATLAS_SAPFinal v8.0_06MAR2018.docx |                 |           |
| Author:   | [name] (Updated [name]; [name]; [name], [name])  | Version Number: | Final 8.0 |
|           |   | Version Date:   | 06MAR2018 |

Template No: CS\_TP\_BS016 – Revision 2  
 Effective Date: 01Feb2010

Reference: CS\_WI\_BS005

Statistical Analysis Plan

---

declared statistically significant.

**7.3. Additional Analyses of Efficacy**

All additional analyses of efficacy will be performed on the ITT Population unless otherwise specified.

**7.3.1. Sensitivity Analyses**

The following sensitivity analyses will be performed:

- Investigator Assessed DFS: DFS defined in a similar manner as defined for the primary analysis, but based on local investigator assessment rather than IRC assessment (Refer to Table 3 of Appendix A for censoring rules.) For this analysis tumor imaging assessments as well as histo-/cytopathology information will be used to assess disease recurrence or occurrence of secondary malignancy. If both imaging and histo-/cytopathological confirmation of recurrence or occurrence of secondary malignancy are available, the earlier of the two dates will be considered. In addition, discordance rates between IRC review and investigator assessments using methods described by Amit et al. will be summarized in a table. Calculations will be as follows:

|                               |  | IRC Review                                  |  |
|-------------------------------|--|---|--|
|                               |  | Recurrence or secondary malignancy or death | No recurrence or secondary malignancy or death |
| Investigator Assessment (INV) | Recurrence or secondary malignancy or death    | a = a1 + a2 + a3                            | b  |
|                               | No recurrence or secondary malignancy or death | c   | d  |

a1: number of agreements on timing and occurrence of event;

a2: number of times agreement on event but INV declares event later than IRC Review;

---

Document: C:\Users\q764206\AppData\Local\Microsoft\Windows\Temporary Internet Files\Content.Outlook\GWW33WM3\ATLAS\_SAPFinal v8.0\_06MAR2018.docx  
 Author: [name] (Updated [name]; [name]; [name], [name])      Version Number: Final 8.0

Version Date: 06MAR2018

Template No: CS\_TP\_BS016 – Revision 2      Reference: CS\_WI\_BS005  
 Effective Date: 01Feb2010

